10.4.3 Sorafenib Dose Reduction

Dose modification will be allowed for subjects with \geq Grade 3 drug-related adverse events. Skin toxicity associated with sorafenib should be managed as shown in [Section 10.2](#), Management of Skin Toxicities (Sorafenib), prior to dose reduction. The dose of sorafenib will be reduced to 400 mg once daily. If toxicities do not resolve, sorafenib may be further reduced to 400 mg once every other day. If a subject is unable to tolerate a dose of 400 mg once every other day due to toxicities thought to be related to sorafenib, treatment should be interrupted. If toxicities resolve to \leq Grade 1, the dose may be re-escalated to the previous dose level at the discretion of the investigator. For management of specific sorafenib-related toxicities, please refer to the sorafenib prescribing information ([Appendix E](#)).

Any modification of study drug administration, and the reason for such action, must be clearly noted on the subject's eCRF (using the Adverse Events reporting page).

10.4.4 Sorafenib Dose Interruption

Subjects with Grade 4 toxicity, or Grade 3 drug-related toxicity that is persistent despite dose reduction and appropriate medical care, should have their treatment interrupted to allow for adequate resolution of the toxicity. Sorafenib may be interrupted for up to 4 weeks. If a subject is able to resume treatment after interruption of \leq 4 weeks, missed doses will not be made up (ie, cycle duration will remain unchanged). If any drug-related toxicity results in interruption of $>$ 4 weeks, the subject should be discontinued from the study unless there is clear benefit from treatment, in which case the investigator must contact the medical monitor to review the subject's condition in order to resume treatment. Subjects removed from treatment for reasons other than radiological evidence of progressive disease should still be followed with regular tumor assessments (see [Section 7.2.4](#)) until disease progression is confirmed by an independent radiology review or start of new treatment, and for survival thereafter.

11 REMOVING SUBJECTS FROM STUDY

Every reasonable effort will be made to keep the subject in the study; however, in the event that a subject withdraws consent from study participation, every effort will be made by the investigator to complete and report the reasons for withdrawal as thoroughly as possible. This evaluation should include final observations, as required by the protocol at the time of the subject's withdrawal. The reason(s) for study termination must be clearly documented in the source documents and on the appropriate page of the eCRF. A Termination eCRF must be completed for any subject who is randomized.

11.1 Criteria for Treatment Discontinuation (Stopping Rules)

Subjects will be discontinued from further treatment with study drug in the event of any of the following:

1. Death
2. Unacceptable toxicity considered by the investigator to require removal of the subject from study treatment.

Note: Adverse events resulting in a subject's permanent discontinuation from the study treatment, regardless of seriousness or relationship to study drug, MUST be promptly reported to the sponsor/designee. Subjects removed from treatment for intolerable toxicity should still be followed with regular tumor assessments (see Section 7.2.4) until disease progression or start of new treatment, and for survival thereafter.

3. Documented progressive disease according to RECIST Version 1.1 at any time during the study.
4. Subjects with radiological evidence of progressive disease per investigator/local radiology assessment should continue treatment until progressive disease is verified by an independent radiologist. Images should be submitted for independent review as soon as possible (see Imaging Manual for specific instructions). Verification of progressive disease is not required in the following circumstance:
 - Significant clinical deterioration that is indicative of progressive disease.
5. Subjects who have documented disease progression will be discontinued from study drug treatment and will continue to be followed up for survival.
6. Clinical progression (eg, symptomatic deterioration) not meeting the RECIST Version 1.1 criteria for radiological evidence of progressive disease but considered by the investigator to require removal of the subject from study. This includes subjects with significant clinical deterioration that is indicative of progressive disease. All related signs and symptoms of clinical progression must be captured in AE eCRF page, the term "progressive disease" should not be recorded as an adverse event or captured on the eCRF page.
7. Treatment interruption for > 4 weeks (ie, total duration of interruption, including the 1 week/cycle break in dosing of tivozanib), unless there is clear benefit from treatment, in which case the investigator must contact the medical monitor to review the subject's condition in order to resume treatment.
8. Requirement for a significant surgical procedure.

Note: Subjects requiring a minor surgical procedure (eg, port placement, skin abscess drainage) may continue on study at the investigator's discretion following discussion with the medical monitor. A brief interruption in therapy (< 4 weeks) may be considered.
9. An intercurrent illness which, in the opinion of the investigator, would prevent completion of study-related evaluations.
10. Significant deviation from the protocol or eligibility criteria. Such subjects will be considered protocol violations and will be removed from study unless there is an exemption granted that is agreed upon between the investigator and the sponsor.
11. Pregnancy.
12. Noncompliance with study or follow-up procedures.
13. Subject withdrawal of consent and election to discontinue the study treatment.

Note: The subject is free to withdraw from the study drug and/or study for any reason and at any time without giving reason for doing so and without penalty or prejudice. In the event of consent withdrawal, the site should make every effort to ensure that the subject is followed for AEs for a

minimum of 30 days after their last dose of study treatment. With documented subject agreement, the investigator will contact the subject for long-term survival follow-up.

14. Termination of the study by the sponsor.
15. Any other reason which, in the opinion of the investigator, would justify removing the subject from the study. In such a case, the investigator's reason for a subject's removal must be recorded on the appropriate eCRF.

Once a subject discontinues study drug treatment for any reason, every effort will be made to collect all clinical and laboratory data as scheduled for the End-of-Treatment Visit and 30-Day Follow-up Visit (see [Section 7.1.7](#) and [Section 7.1.8](#)) as well as long term response and survival follow-up ([Section 7.1.10](#)).

Subjects who are discontinued from study drug for reasons other than progression by RECIST Version 1.1 will undergo scans for tumor assessment according to the original tumor assessment schedule until any of the following occurs, whichever comes first: PD per RECIST Version 1.1 (as confirmed by independent radiology review), initiation of new anti-cancer treatment, or discontinuation of the subject from overall study participation (death, subject withdrawal of consent, loss to follow-up, or study closure).

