7.1 Procedures/Parameters to be Measured

See the Study Flowchart ([Table 1](#), beginning on page 12) for the timing of the procedures to be performed at each visit.

All subjects will be assessed by scheduled clinical, laboratory, and other diagnostic assessments throughout the study. Subjects will be treated on an outpatient basis, unless hospitalization is required for other reasons.

Subjects must voluntarily sign and date the study-specific Institutional Review Board (IRB)/Ethics Committee (EC)-approved informed consent before any study-related procedures (with the exception of disease assessment for screening if it was completed as part of standard of care) are performed.

All screening assessments are to be performed within **21 days** prior to first study drug dose, unless otherwise specified.

The day of first study drug administration will be considered **Day 1** of the study.

Clinic visits will take place according to the schedule of assessments. The visit window of ± 2 working days does not apply to study drug administration. Visit assessments will be performed prior to administration of the study drug for that day.

If significant changes from baseline are noted during the course of the study, additional unscheduled clinic visits may be undertaken by the investigator, or requested by the sponsor, in order to determine both the relevance of the finding(s) and the duration of the event(s).

All end-of-treatment assessments are to be performed within **7 days** following the last study drug dose unless delayed due to the occurrence of an adverse event. Note: subjects starting any new anti-cancer therapy must complete the End-of-Treatment Visit prior to starting the new anti-cancer therapy.

A follow-up visit will be performed **30 days (± 7 days)** following the last dose of study drug.

After the 30-Day Follow-up visit, subjects will be contacted once every 3 months by the site to collect long-term survival data.

Informed Consent

All subjects must take part in the informed consent process. Adequate time must be allowed for the subject to ask questions and make a voluntary decision. No protocol specific procedures, including screening procedures are to be performed until the subject has signed and dated an IRB/EC approved informed consent form (ICF). The signing of the ICF can occur outside of the 21-day screening period; however, all protocol related procedures must only be performed after signing of the consent.

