7.1.10 Long Term Response and Survival Follow-Up

- All subjects will be followed until death from any cause (unless the subject is lost to follow-up, withdraws consent for the entire study, or the Sponsor terminates the study early). After the 30-Day Follow-up visit, subjects will be contacted once every 3 months by the site to collect long-term survival data. Additional contacts may be made to support key analyses, such as the analysis of overall survival at the time of the final PFS analysis, and the final analysis of overall survival.
- Response assessment (CT scan or MRI scan): for subjects with ongoing objective response or disease stabilization at the time of treatment discontinuation, who discontinue for reasons other than radiological evidence of progressive disease, tumor assessments will continue to be collected (every 2 months during the first year [beginning from the date of the last scan performed prior to treatment discontinuation], every 3 months during the second year, and every 6 months thereafter) until disease progression is confirmed by independent radiology review or the start of another anti-cancer therapy (see [Section 7.2.4](#)).

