7.2.5 Duration of Follow-Up

Follow-up safety evaluations will be conducted 30 days following the subject's last dose of study drug. This period will be extended if any observed toxicity, thought to be associated with study drug, has not resolved or returned to baseline.

Note: The occurrence of any significant post-therapy event thought to be associated with study drug must be reported to the sponsor.

Subjects starting any new anti-cancer therapy must complete the End-of-Treatment Visit prior to starting the new anti-cancer therapy. Adverse Event Assessment will be conducted in order to confirm that all events have resolved, stabilized, or returned to baseline and that no longer-term deleterious effects of study drug administration have become evident.

In the event that a subject has an ongoing objective response or disease stabilization at the time of treatment discontinuation, who discontinues for reasons other than radiological evidence of progressive disease (per RECIST Version 1.1, as confirmed by independent radiology review), tumor assessments will continue to be collected (every 2 months during the first year [beginning from the date of the last scan performed prior to treatment discontinuation], every 3 months during the second year, and every 6 months thereafter) until disease progression (per RECIST Version 1.1) is confirmed by independent radiology review

the start of another anti-cancer therapy, or discontinuation of the subject from overall study participation (ie, death, subject withdrawal of consent, or loss to follow-up, or study closure).

After discontinuation from all study treatment, follow-up information for long-term survival and subsequent anti-cancer therapy, if available, will be obtained every 3 months from the End of Treatment Visit or 30-Day Follow-up Visit (whichever is later) until death, withdrawal of consent, loss to follow-up, or study closure, whichever occurs first. Additional contacts may be made to support key analyses, such as the analysis of overall survival at the time of the final PFS analysis, and the final analysis of overall survival.

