9 ASSESSMENT OF ACTIVITY

9.1 Disease Classification and Response Assessments

Data on disease classification and the duration of disease stabilization or any objective response, as well as the time to disease progression, will be collected for all subjects. Subjects will undergo disease assessment at screening (within 30 days prior to first dose of study drug) and every 8 weeks following Cycle 1, Day 1 until radiological disease progression is documented and confirmed by independent radiology review. Response will be determined by RECIST (Version 1.1) criteria ([Appendix A](#)).

Disease parameters to be assessed:

- Disease classification
- Diagnostic imaging/measurement of target lesions
- Response assessment.

Disease Classification

Details of the primary diagnosis should be documented at the Screening Visit. The histological/cytological type and stage of disease should be noted on the eCRF.

Diagnostic Imaging/Measurement of Lesions

Subjects should be followed with the same imaging procedure throughout this study; if progressive disease (PD) is documented at any time per RECIST Version 1.1, no further imaging or lesion measurements will be required after PD is verified by an independent radiologist; diagnostic studies documenting response must be available for sponsor review.

Response Assessment

Response will be assessed as detailed in [Appendix A](#) using RECIST criteria Version 1.1. All subjects who receive a minimum of 2 cycles of study drug will be considered evaluable for response assessment. All subjects who develop early progressive disease (regardless of the

duration of the study treatment) prior to response evaluation will be considered to have progressed on study.

The duration of any objective response is to be measured from the date the initial response is observed to the date that disease progression is observed. In the case of SD, follow-up assessments must have met the SD criteria at least once after study entry, at a minimal interval of 8 weeks.

Response Assessment Update

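### SAP 3.2.1 censors overall survival at randomization when no scan was done; read literally this discards known deaths and contradicts protocol 14.3.4, and the PFS no-scan bullet also lacks a death exception

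*Protocol*

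**What the plan says.** **OS.** SAP 3.2.1 defines OS as time from randomization to death from any reason, then gives two censoring bullets. The first censors at randomization when there is no tumor assessment after randomization, with no further condition. The second censors at the date last known alive when death is not confirmed. Protocol 14.3.4 (definition of efficacy endpoints) has no scan condition. It censors at the date last known alive, and at randomization only for subjects without any later data.

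**PFS.** SAP 3.2.1 counts death from any reason as an event, but its no-scan bullet censors at randomization without excepting deaths. Protocol 14.3.4 gives two further rules. The endpoint definition censors unscanned subjects at randomization only if no death is known. Missing-data rule (b) spares only deaths before the second scheduled tumor assessment.

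**Who can lack a scan.** On-study scans run "every 8 weeks following Cycle 1, Day 1 until radiological disease progression is documented" (protocol 9.1), and "The day of first study drug administration will be considered" Day 1 (protocol 7.1). The rule closing protocol 11.1 is for subjects who have stopped drug: "Subjects who are discontinued from study drug for reasons other than progression by RECIST Version 1.1 will undergo scans for tumor assessment". A subject randomized but never dosed therefore has no scheduled scan. SAP 4.10 confirms that some subjects were not dosed, and gives no number. Survival follow-up has no dosing condition: "All subjects will be followed until death from any cause" (protocol 7.1.10).

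**The concern.** A tumor scan tells us about progression, not about whether the subject is alive. A rule that makes OS censoring depend on a scan can set aside a death that the site has recorded, and can reduce months of documented survival to zero. It affects two groups: randomized subjects who were never dosed, and dosed subjects who die before any post-baseline scan. Both stay in the ITT population, which is all randomized subjects.

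OS is the first secondary endpoint and has only about 61% planned power. Its final analysis is triggered by follow-up status (all subjects lost, withdrawn or dead, or at least 2 years on study for those still followed) and not by an event count. Deaths removed by the censoring rule would therefore not be replaced by waiting longer.

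For PFS the stake is clarity: a death in an unscanned subject has no single agreed treatment in the primary analysis.

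**Working it through.** **Rules side by side, for a subject with no scan after randomization** (week 30 is only an illustration)

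| Situation | Protocol 14.3.4 | SAP 3.2.1 no-scan bullet, literally |
|---|---|---|
| OS, death at week 30 | event at week 30 | censored at randomization |
| OS, last known alive at week 30 | censored at week 30 | censored at randomization |
| OS, nothing known later | censored at randomization | censored at randomization |
| PFS, death at week 30 | endpoint definition: event; rule (b): censored at randomization | censored at randomization, against the SAP's own PFS definition |

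Under rule (b) the second scheduled assessment is week 16 (2 × 8) from Cycle 1 Day 1. For a never-dosed subject it has no date at all.

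**Reproducing the plan's OS power.** Inputs (protocol 14.2, SAP 4.9): medians 12 and 16 months, so HR = 12/16 = 0.75; 245 events at the final analysis; one-sided 2.5%; 1:1 allocation. By Schoenfeld's formula, power = Φ(½·√d·|ln HR| − 1.960).

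- d = 245: ½ × 15.65 × 0.2877 = 2.251; 2.251 − 1.960 = 0.291; Φ = 61.5%. The plan states about 61%, so the figure reproduces.

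**Loss from never-dosed subjects.** The count is an assumption: 5 per arm, close to the planned 3% dropout (0.03 × 161 = 4.8), used only for scale. Exponential survival, 24 months of follow-up:

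- P(death by 24 months) = 1 − 2^(−24/12) = 0.750 and 1 − 2^(−24/16) = 0.646.
- Deaths lost = 5 × 0.750 + 5 × 0.646 = 7.0.
- d = 238: ½ × 15.43 × 0.2877 = 2.219; 2.219 − 1.960 = 0.259; Φ = 60.2%.

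Using the plan's overall death fraction instead, 10 × 245/322 = 7.6 deaths are lost and power is 60.1%. For 1 to 16 never-dosed subjects in total (0.3% to 5% of 322), 0.8 to 12.2 deaths are lost and power is 61.3% to 59.3%.

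**Rough ceiling for deaths before a first scan.** Eight weeks is 56 × 12/365.25 = 1.84 months. At the planned medians, 1 − 2^(−1.84/12) = 10.1% and 1 − 2^(−1.84/16) = 7.7% die by then. That is 161 × (0.101 + 0.077), about 29 subjects. If none had an earlier scan, d = 216 and power is about 56%. The true loss should be well below this: protocol 7.1.7 asks for an end-of-treatment scan, and eligibility requires a life expectancy of at least 3 months.

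**The case against.** The strongest reply is that censoring rules apply only to subjects without an event. A competent programmer would code the death first and then censor the rest, so no death would be lost. That is probably what would happen, but the text does not say so. The second OS bullet carries a condition about death and the first does not, and nothing sets an order between them. Even on this reading, an unscanned subject known to be alive loses all documented survival time, contrary to the protocol.

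A second reply is that survival is collected regardless of dosing. Protocol 7.1.10 follows everyone until death, and extra contacts are allowed for the OS analyses. This stands. It means that the fault lies in the analysis rule and not in data collection, which also makes it easy to correct.

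A third reply is that the SAP already deals with never-dosed subjects. SAP 4.10 added an exploratory PFS analysis in the safety population, but that analysis leaves these subjects out and does not concern OS. Sensitivity Analysis #2 counts any death as a PFS event, which helps for PFS, but it is not the primary analysis.

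Finally, the effect is small and the number affected is not stated. That stands, and it sets the severity.

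**Conclusion.** The SAP's OS no-scan bullet is wrong as written and contradicts the protocol. The PFS no-scan bullet is inconsistent with the SAP's own definition and with the protocol's endpoint definition, and rule (b) adds a third version. Severity is minor. The cost is about 7 of 245 deaths and 1.3 points of OS power (61.5% to 60.2%). This assumes 5 never-dosed subjects per arm, exponential survival at the planned medians, and a literal reading. Early deaths before a first scan would add an unknown amount.

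A reader might infer more, but the documents do not support it:

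- *That never-dosed subjects drop out of survival follow-up.* Protocol 7.2.5 times the 3-monthly contacts from the End of Treatment or 30-Day visit, so a start date is missing for them. The duty to follow them until death is not.
- *That protocol 11.1 items 10 and 15 take subjects out of follow-up.* Their wording ("Such subjects will be considered protocol violations and will be removed from study unless there is an exemption granted"; "Any other reason which, in the opinion of the investigator, would justify removing the subject from the study") is loose. However, the list opens with "Subjects will be discontinued from further treatment with study drug in the event of any of the following", and its closing paragraph ends overall participation only for death, withdrawn consent, loss to follow-up or study closure. Nothing shows that item 10 produced the never-dosed subjects either; SAP 4.10 attributes them to external issues.
- *That the PFS hazard ratio is biased.* This would need never-dosed status to be both related to prognosis and unequal between arms. The documents give no count, no split by arm and no link to prognosis.

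**What to change.** 1. SAP 3.2.1, OS: delete the tumor-assessment bullet. State that every known death is an event and that all other subjects are censored at the date last known alive, or at randomization only if there are no later data.
2. SAP 3.2.1, PFS: restrict the no-scan bullet to subjects with *no post-randomization tumor assessment and no known death*.
3. Protocol 14.3.4, missing-data rule (b): align it with the PFS endpoint definition in the same section, so that any known death in an unscanned subject is an event. Copying rule (b) into the SAP would leave the conflict in place.

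The cost is two SAP bullets and one protocol sentence. No new data are needed, because deaths and last-contact dates are already collected, and the OS change can serve both the interim and the final OS analysis. One consequence should be accepted openly: a late death in a subject never scanned becomes a PFS event at the date of death, as Sensitivity Analysis #2 already treats it. No change to the scan schedule is proposed, since scans missed before the 04 October 2018 cut-off cannot be recovered.
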